13.5.1.3. PIN

Statistical Analyses
PIN (Q2M arm only)
Endpoints
Change from Month 2(OLI)/Month 1(D2I) in the PIN acceptance score at: 
 Month 12(OLI)/Month 11(D2I) Month 6(OLI)/Month 5(D2I)
Statistical Test

 The Wilcoxon Signed-Rank Test will be used to evaluate whether the change from Month 2/Month 1 to Month 6(OLI)/Month 5(D2I), and to Month 12(OLI)/Month 11(D2I), respectively, is statistically different from zero based on a two-sided significance level of 0.05. Separate tests will be performed for the change at each time point.

Statistical Analyses
Dataset

 OC (Observed Case) dataset (with data slotting for the withdrawal/unscheduled visits) will be used. see Section 16.3.4 for details. No additional imputations will be used.
Results Presentation

 Summary statistics at each analysis timepoint and p-value for each comparison.

14. VIROLOGY

Given data availability, the virology analyses will mainly use genotype and phenotype data based on plasma sample for CVF population, unless otherwise specified. Summary tables (if applicable) will be based on the mCVF population. Listings will include all CVFs in this study. Additional analyses for HIV-1 resistance may be carried out on peripheral blood mononuclear (PBMC) samples and/or on stored blood samples from relevant time points.

If pre-treatment genotypic/phenotypic results are available from both the central laboratory and Monogram Biosciences, then Monogram assays will take precedence.

Table 5 provides an overview of the planned analyses. Further details of the planned displays are provided in Appendix 15: List of Data Displays and will be based on GSK Data Standards and statistical principles.

Table 5 Overview of Planned Virology Analysis

Endpoint	Absolute			
	Summary		Individual	
	T	F	F	L
Genotypic resistance at time of CVF^[1]				
Prevalence of Resistance Mutations	Y ^[2]			Y
Prevalence of Genotypic Susceptibility	Y			
Phenotypic resistance at time of CVF^[1]				
Prevalence of Phenotype	Y ^[3]			Y
Fold Change to CAB, RPV and BIC	Y			Y ^[4]
IN, PR/RT Replication Capacity ^[5]				Y
Other				
Viral load, Genotypic and Phenotypic data for Participants with genotype and/or phenotype data for CVF and non-CVF participants				Y ^[4]
Net Assessment	Y			

NOTES:

- T = Table, F = Figure, L = Listing, Y = Yes display generated.

16. APPENDICES

16.1. Appendix 1: Protocol Deviation Management and Definitions for Per Protocol Population

16.1.1. Exclusions from Per Protocol Population

Important protocol deviations leading to exclusion from the Per Protocol population are those deviations which may

- directly impact the efficacy endpoint of HIV-1 RNA; or
- lead to permanent discontinuation of IP/withdrawal and hence indirectly impact the efficacy endpoint by causing data to be missing.

The following criteria define the protocol deviations which, if they occur prior to an analysis timepoint of interest (e.g. Month 12 or Month 6), will lead to exclusion of a participant from the Per-Protocol population for that analysis. Potential protocol deviations leading to exclusion from PP population will be reviewed by the study team to confirm that they meet these criteria. A final review will occur before the clinical database has been frozen for analysis.

A participant meeting any of the following criteria will be excluded from the Per Protocol population **based on case-by-case clinical determination**. Note exclusion category # 2 below will only be applied in the Month 12 analysis. Other categories will be applied in both Month 6 and Month 12 analysis.

Number	Exclusion Description
01	Participant deviates from inclusion or exclusion criteria that may significantly affect exposure, response to therapy or participant safety or that are fundamentally inconsistent with the intended study population, as recorded in the Protocol Deviation form in the eCRF based on study team review (where indicated in the PDMP as case-by-case determination).
02*	
For Month 12 analysis only:
 
Participant has non-compliance with IP (including IM dosing errors) or took/received incorrect IP (i.e., other than the one to which they were randomized) up to an analysis timepoint of interest, meeting the following conditions during the Maintenance Phase:
 
 1. Two or more injection intervals affected by over dosage deviations, for example 
 • Extra injection or excessive volume administered • Length of time between injections less than 21 days between the first and second injections (between M1 and M2 for OLI; between Day 1 and M1 for D2I), or less than 52 days for all subsequent dosing intervals, excluding split doses up to the analysis visit of interest (M12 for OLI /M11 for D2I) 
* 21 = 28 – 7; 52 = 28 + 31 – 7 (smallest possible dosing interval allowed – 7 days)
 2. At least 10% of total time on-treatment with under dosing deviations in the Maintenance Phase up to the analysis visit of interest (i.e. Month 12 for OLI and BIK/Month11for D2I), where the % of non-compliance is calculated as: (total number of non-compliant dosing days / total number of intended exposure days) * 100%

Number	Exclusion Description
	
Where :
 
 • Total number of intended exposure days = date of the last analysis timepoint snapshot viral load (up to Injection Study Day 372 for OLI subjects, up to Study Day 372 for D2I subjects and up to Study Day 378 for BIK subjects) – Start Date of Study Treatment + 1 • Total number of non-compliant dosing days up to the analysis timepoint visit (or date of IP discontinuation/ withdrawal, whichever is earlier), is derived as follows: BIK Arm: 
 ○ Duration of interruptions in BIK arm for reasons other than treatment-related adverse events/laboratory abnormalities (based on Exposure eCRF forms) Q2M Arm: 
 ○ Length of time (in days) in excess until next injection from date of dosage/administration deviation potentially resulting in under dosage. Examples include: 
 - less than 3 ml administered - early stop of oral bridging prior to the next planned injection ○ Length of time (in days) in excess beyond 31 days between the first and second injections and beyond 69 days for all subsequent dosing intervals. 
 * 69 = 31+ 31 + 7 (largest possible dosing interval allowed + 7 days) - For those with oral bridging (OB), length of time (in days) is calculated between the start of oral bridging and the preceding injection ○ Interrupted days in oral study treatment (oral lead-in or oral bridging) if the oral dose has been interrupted for 3 or more consecutive days and the primary interruption reason is not adverse event or laboratory abnormality (based on the eCRF Exposure forms). 3 days will be assumed if such interrupted days are not available in the database.
03	
Prohibited medications: receiving ART medication other than that prescribed/allowed by the study (excluding permanent changes in ART regimen; such cases will be retained as 'HIV1-RNA ≥ 50 c/mL' in the per protocol snapshot analysis) or receiving prohibited concomitant medication that would impact exposure or response to therapy with duration and route of administration taken into consideration, as recorded in the Protocol Deviation form in the eCRF based on study team review (where indicated in the PDMP as case-by-case determination)

04	
Permanent discontinuation of IP/withdrawal due to a reason of "Protocol Deviation" (as recorded in the eCRF Conclusion form).

05	
Other important protocol deviations that exclude participant from Per Protocol population as recorded in the Protocol Deviation form in the eCRF based on study team review (where indicated in the PDMP as case-by-case determination).

* Note: Category 02 is only applicable to the Month 12 analysis.
	

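### The SAP gives two rules for Per-Protocol exclusion, one automatic and one case-by-case, and does not mask the deciding team to viral load, so Per-Protocol membership could depend on outcome.

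*SAP*

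**What the plan says.** SAP Section 16.1.1 states the rule in three ways.

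- **Automatic.** Listed deviations that occur before the analysis timepoint "will lead to exclusion of a participant from the Per-Protocol population for that analysis". The review has a narrow task: "Potential protocol deviations leading to exclusion from PP population will be reviewed by the study team to confirm that they meet these criteria".
- **Discretionary.** The paragraph introducing the table says that a participant meeting any criterion is excluded "based on case-by-case clinical determination", with no category exempted.
- **Mixed.** In the table, categories 01, 03 and 05 are decided "based on study team review (where indicated in the PDMP as case-by-case determination" (the PDMP is the Protocol Deviation Management Plan). Categories 02 and 04 carry no such clause. Category 02 uses counts and thresholds, such as "At least 10% of total time on-treatment with under dosing deviations in the Maintenance Phase". Category 04 is read from the eCRF Conclusion form: "Permanent discontinuation of IP/withdrawal due to a reason of" protocol deviation.

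On timing, Section 4.1 places the deviation review before unblinding and database freeze, and Section 16.1.1 places a final review before freeze. Section 2.3 describes the trial as open-label. Sections 5.5.2 and 7.1.5.1 make the Per-Protocol analysis a sensitivity analysis, compared with the primary mITT-E result for consistency. Section 7.2.5.1 repeats it for the key secondary endpoint.

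**The concern.** Under the automatic rule, meeting a criterion settles the matter. Under the discretionary rule it only opens a decision, so two participants with the same computed non-compliance could be treated differently.

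That would be a drafting matter if the deciding team could not know outcomes, but the SAP does not provide for this. Review before unblinding does not in itself hide accruing viral loads in an open-label trial. The Month 6 deliverables include subject-level Snapshot outcomes and all HIV-1 RNA data (Section 16.15.11, Listings 8 and 10) and treatment assignment (Section 16.15.12, Listing 23). Section 3.1 restricts access to the Month 6 results for participants and most investigators, and says nothing about the sponsor's study team.

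At stake is the value of the Per-Protocol analysis as a check on non-inferiority. If membership can depend on who rebounded, agreement with the primary result says less than it appears to.

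**Working it through.** The SAP gives no figure for the effect of Per-Protocol exclusions, so there is none to reproduce. The thresholds inside category 02 do agree with their own footnotes: 28 − 7 = 21, 28 + 31 − 7 = 52, 31 + 31 + 7 = 69.

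**Step 1: what discretion can do in each category.** The discretionary sentence applies to participants who meet a criterion.

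- Categories 02 and 04: the criterion is (largely) fixed by data. The automatic rule would exclude everyone who meets it, so discretion can only keep people in.
- Categories 01, 03 and 05: whether the criterion is met is itself a judgement, so discretion can also take people out. One guard exists: category 03 keeps permanent ART changes in the analysis as failures.

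**Step 2: inputs.** About 654 randomised 2:1 (Section 2.3) gives 436 and 218. Section 2.1 removes 11 participants from one site, leaving 643; if they split 2:1 (assumption), 429 and 214. The margin is 4% on the upper limit of the two-sided 95% CI (Section 5.5.1). All failure counts below are assumptions.

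**Step 3: formula.** Section 7.1.5.1, taken as one stratum with x/n failures on Q2M and y/m on BIK, N = n + m:

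- d = x/n − y/m; W = nm/N
- P = [n²y − m²x + nm(m − n)/2]/N²
- Q = [x(m − y)/N + y(n − x)/N]/2
- upper limit = d + 1.96 √(dP + Q)/W

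**Step 4: selective retention (02 and 04).** Suppose three Q2M failures remain and 20 Q2M non-failures who meet a criterion are either kept or excluded.

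- Kept: 3/433 = 0.69%
- Excluded: 3/413 = 0.73%
- Change in the Q2M rate: about 0.03 points

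Against 2/218 on BIK, the upper limit is 1.26% with them kept and 1.32% with them excluded.

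**Step 5: selective removal (01, 03 and 05), near the margin.**

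- 13/429 vs 2/214: d = 2.096%, W = 142.78, P = −24.42, Q = 2.790; standard error 1.057%; upper limit 2.096 + 1.96 × 1.057 = 4.17%, not met.
- One Q2M failure removed, 12/428 vs 2/214: d = 1.869%, standard error 1.034%; upper limit 3.90%, met.

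With 0 to 4 BIK failures the pattern is the same. One Q2M failure above the largest passing count gives 4.06% to 4.17%, and removing it gives 3.77% to 3.90%.

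**Step 6: selective removal, away from the margin.** With 4/429 vs 2/214, removing 0, 1, 2 or 3 Q2M failures gives upper limits of 1.58%, 1.28%, 0.98% and 0.67%. Each step is about 0.3 points and the conclusion does not change.

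**The case against.** **The two sentences may be one rule.** The case-by-case determination could be read as the confirmation step described just before it, and the PDMP, which is not at hand, may narrow categories 01, 03 and 05. This is possible, but the table attaches case-by-case review to 01, 03 and 05 only, while the sentence above it covers every category. For 02 and 04 the text as written leaves discretion after the criterion is met.

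**Nothing shows that the team sees viral loads.** This stands. Randomisation codes are distributed after freeze (Section 3.2), and Sections 16.11 and 16.12 call the pre-freeze adverse event review blinded. The use of outcomes is a risk inferred from the open-label design and the Month 6 outputs.

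**Category 02 is not fully mechanical.** This also stands. Its over-dosing and under-dosing lists are given as examples, so someone must judge whether a dosing event counts. That judgement concerns whether the criterion is met, and does not call for further discretion afterwards.

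**Selective handling could be traced.** Exclusions are tabulated (Table 1.10) and listed (Listing 5), alongside listings of deviations, Snapshot outcomes, viral loads and dosing errors. This allows a later check but does not prevent the problem.

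**A stronger reading to avoid.** A reader might infer that discretion over dosing deviations could reverse the sign of the treatment difference. For example, 6/436 vs 2/218 (+0.46 points, upper limit 2.13%) becomes 3/433 vs 2/218 (−0.22 points, upper limit 1.26%) if three Q2M failures are dropped. The documents do not support this. If those three meet category 02 or 04, the automatic rule drops them as well, so the shift is not an effect of discretion. Both limits are also below 4%, and the sign of the estimate is not the non-inferiority criterion.

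**Conclusion.** The concern holds as an inconsistency that leaves avoidable room for outcome-dependent Per-Protocol membership. Review before unblinding and freeze limits when decisions are made, not what the deciding team may know.

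Its reach is limited. The primary mITT-E and supportive ITT-E analyses are untouched. For categories 02 and 04 the effect is selective retention, about 0.03 points on the Q2M rate in the example of 20 retained Q2M non-failures. Keeping a Q2M failure would count against Q2M, whereas keeping a BIK failure could favour it. Outcome-dependent removal is possible mainly in 01, 03 and 05, at roughly 0.3 points on the upper limit per Q2M failure. It changes the Per-Protocol conclusion only when the limit is already close to 4%.

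These sizes rest on assumed failure counts, a single stratum and, for the 429 and 214 figures, a 2:1 split of the 11 site exclusions. The change is worth making because it costs almost nothing and makes the planned consistency check more credible.

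**What to change.** In SAP Section 16.1.1:

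1. **Categories 02 and 04.** Delete the case-by-case clause, so that criterion met means excluded. In 02, confine judgement to whether a dosing event counts as an over- or under-dosing deviation, decided without viral-load results.
2. **Categories 01, 03 and 05.** Have the existing study team decide from deviation records with post-baseline HIV-1 RNA and Snapshot outcome withheld. Lock those decisions before the Month 12 Snapshot dataset is derived.
3. **Order of work.** Compute the category 02 percentage afterwards. Its denominator uses the date of the Snapshot viral load, but not the result.
4. **Threshold wording.** A strict rule needs a single threshold. Section 16.1.1 excludes at 10% or more of intended exposure days, whereas the treatment compliance entry in Section 16.6.2 uses more than 10% of exposure. Reconcile the two.

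The cost is SAP wording and a deviation listing without viral-load columns, with no extra staff. The downside is that a few participants the team might have kept will be excluded.

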16.2. Appendix 2: Schedule of Activities

Time and Events Table for CAB LA + RPV LA Oral Lead In (OLI) Participants:

Procedure	Screening Visit ^a	Maintenance Phase									Extension Phase	Withdrawal Assessments ^y	Long-Term Follow-up ^z	
		Day 1 ^b	Month											
			1 ^c	2	4	6	8	10	12	Q2M after Month 12				
Written Informed Consent	X													
Eligibility Verification (Inclusion/ Exclusion Criteria)	X	X ^d												
Randomization		X												
Demography	X													
Medical History ^e	X													
Cardiovascular risk assessment ^e	X	X								X		X		
Medication History/ Prior ART history	X													
Syphilis serology + reflex Rapid Plasma Reagin (RPR)	X	X												
Symptom Directed Physical Exam and Medical Assessment ^f	X	X	X	X	X	X	X	X	X	X	X	X	X	
Weight, Height and BMI ^g		X		X	X	X				X		X		
Waist Circumference		X		X	X	X				X		X		
Hip Circumference		X		X	X	X				X		X		
Vital Signs (BP, HR, Temperature) ^h	X	X		X	X	X				X		X		
CCI														
12-lead ECG ⁱ (triplicate at Day 1 pre-dose)	X	X	X							X		X		
CDC HIV-1 stage ^{ff}	X	X												
HIV Associated Conditions		X	X	X	X	X	X	X	X	X	X	X	X	
AEs, SAEs, Concomitant Medications	X ⁱ	X	X	X	X	X	X	X	X	X	X	X	X	
ISR Assessment for IM injection			X	X	X	X	X	X	X	X	X	X	X	

Procedure	Screening Visit ^a	Maintenance Phase								Extension Phase	Withdrawal Assessments ^y	Long-Term Follow-up ^z
		Day 1 ^b	Month									
			1 ^c	2	4	6	8	10	12	Q2M after Month 12		
Columbia Suicide Severity Rating Scale (eC-SSRS) ^k	X	X		X		X			X		X	
Clinical chemistry and Hematology	X	X	X	X	X	X	X	X	X	X	X	X
Pregnancy Testing ^l	S	U	U	U	U	U	U	U	U	U	S	U
HIV-1 RNA and sample for storage (S) ^m	X	X	X	X	X	X	X	X	X	X	X	X
HIV-1 RNA low copy sample		X							X			
CD4+ cell count	X	X	X	X	X	X	X	X	X	X	X	X
CD8+ cell count		X				X			X		X	
Urinalysis ⁿ		X	X			X			X		X	
Fasting Labs Glucose, Cholesterol (Total, HDL and LDL) and Triglycerides ^o		X				X			X		X ^p	
Hepatitis B (HBsAg), Anti-HBc, and Anti-HBsAG, Hepatitis C (anti-HCV Ab)	X											
PT/PTT/INR	X	X										
Whole Blood (Virology)		X				X			X		X	
CCI												
PBMCs ^q		X				X			X		X	
Insulin, HbA1c and renal, and bone biomarker analytes (blood urine) ^r		X				X			X		X ^s	
CCI												
Genetics sample ^t		X										
PK sampling ^u (S)=Storage only			S	S	S	S	S	S	S		X	S
Oral CAB and Oral RPV Dispensation ^v		X										

Procedure	Screening Visit ^a	Maintenance Phase								Extension Phase	Withdrawal Assessments ^y	Long-Term Follow-up ^z	
		Day 1 ^b	Month										Q2M after Month 12
			1 ^c	2	4	6	8	10	12				
IP accountability (Pill Counts)			X										
IM treatment administration ^w			X	X	X	X	X	X	X	X			
HIV TSQs ^{cc}		X				X				X	X ^{dd}		
HIV TSQc ^{cc}										X	X ^{dd}		
CCI													
Preference ^{cc}									X		X ^{dd}		
PIN ^{cc}				X		X			X		X ^{dd}		
CCI													
History of Cosmetic procedures ^{gg}									X		X		

Time and Events Table for CAB LA + RPV LA Direct to Injection (D2I) Participants:

Procedure	Screening Visit ^a	Maintenance Phase							Extension Phase	Withdrawal Assessments ^y	Long-Term Follow-up ^z
		Day 1 ^b	Month						Q2M after Month 11		
			1 ^c	3	5	7	9	11			
Written Informed Consent	X										
Eligibility Verification (Inclusion/ Exclusion Criteria)	X	X ^d									
Randomization		X									
Demography	X										
Medical History ^e	X										
Cardiovascular risk assessment ^e	X	X						X			
Medication History/ Prior ART history	X										
Syphilis serology + reflex Rapid Plasma Reagin (RPR)	X	X									
Symptom Directed Physical Exam and Medical Assessment ^f	X	X	X	X	X	X	X	X	X	X	X
Weight, Height and BMI ^g		X	X	X	X			X		X	
Waist Circumference		X	X	X	X			X		X	
Hip Circumference		X	X	X	X			X		X	
Vital Signs (BP, HR, Temperature) ^h	X	X	X	X	X			X		X	
CCI											
12-lead ECG ⁱ (triplicate at Day 1 pre-dose)	X	X						X		X	
CDC HIV-1 stage ^{ff}	X	X									
HIV Associated Conditions		X	X	X	X	X	X	X	X	X	X
AEs, SAEs, Concomitant Medications	X ^j	X	X	X	X	X	X	X	X	X	X
ISR Assessment for IM injection		X	X	X	X	X	X	X	X	X	X
Columbia Suicide Severity Rating Scale (eC-SSRS) ^k	X	X	X		X			X		X	

CONFIDENTIAL

213500

Procedure	Screening Visit ^a	Maintenance Phase							Extension Phase	Withdrawal Assessments ^y	Long-Term Follow-up ^z
		Day 1 ^b	Month						Q2M after Month 11		
			1 ^c	3	5	7	9	11			
Clinical chemistry and Hematology	X	X	X	X	X	X	X	X	X	X	X
Pregnancy Testing ^l	S	U	U	U	U	U	U	U	U	S	U
HIV-1 RNA and sample for storage (S) ^m	X	X	X	X	X	X	X	X	X	X	X
HIV-1 RNA low copy sample		X						X			
CD4+ cell count	X	X	X	X	X	X	X	X	X	X	X
CD8+ cell count		X			X			X		X	
Urinalysis ⁿ		X	X		X			X		X	
Fasting Labs: Glucose, Cholesterol (Total, HDL and LDL) and Triglycerides ^o		X			X			X		X ^p	
Hepatitis B (HBsAg), Anti-HBc, and Anti-HBsAG, Hepatitis C (anti-HCV Ab)	X										
PT/PTT/INR	X	X									
Whole Blood (Virology)		X			X			X		X	
CCI											
PBMCs ^q		X			X			X		X	
Insulin, HbA1c and renal, and bone biomarker analytes (blood urine) ^r		X			X			X		X ^s	
CCI											
Genetics sample ^t		X									
PK sampling ^u (S)=Storage only			S	S	S	S	S	S		X	S
IM treatment administration		X	X	X	X	X	X	X	X		
HIV TSGs ^{cc}		X			X			X		X ^{dd}	
HIV TSGc ^{cc}								X		X ^{dd}	
CCI											
Preference ^{cc}								X		X ^{dd}	

Procedure	Screening Visit ^a	Maintenance Phase							Extension Phase	Withdrawal Assessments ^y	Long-Term Follow-up ^z
		Day 1 ^b	Month						Q2M after Month 11		
			1 ^c	3	5	7	9	11			
PIN ^{cc}			X		X				X	X ^{dd}	
CCI											
History of Cosmetic procedures ⁹⁹								X		X	

Time and Events Table for BIK Participants:

Procedure	Screening Visit ^a	Maintenance Phase							Withdrawal Assessments ^y
		Day 1 ^b	Month						
			2	4	6	8	10	12 ^{bb}	
Written Informed Consent	X								
Eligibility Verification (Inclusion/ Exclusion Criteria)	X	X ^d							
Randomization		X							
Demography	X								
Medical History ^e	X								
Cardiovascular risk assessment ^e	X	X						X	
Medication History/ Prior ART history	X								
Syphilis serology + reflex Rapid Plasma Reagin (RPR)	X	X							
Symptom Directed Physical Exam and Medical Assessment ^f	X	X	X	X	X	X	X	X	X
Weight, Height and BMI ^g		X	X	X	X			X	X
Waist Circumference		X	X	X	X			X	X
Hip Circumference		X	X	X	X			X	X
Vital Signs (BP, HR, Temperature) ^h	X	X	X	X	X			X	X
CCI									
12-lead ECG ⁱ (triplicate at Day 1 pre-dose)	X	X						X	X
CDC HIV-1 stage ^{ff}	X	X							
HIV Associated Conditions		X	X	X	X	X	X	X	X
AEs, SAEs, Concomitant Medications	X	X	X	X	X	X	X	X	X
Columbia Suicide Severity Rating Scale (eC-SSRS) ^k	X	X	X		X			X	X
Clinical chemistry and Hematology	X	X	X	X	X	X	X	X	X
Pregnancy Testing ^l	S	U	U	U	U	U	U	U	S
HIV-1 RNA and sample for storage (S) ^m	X	X	X	X	X	X	X	X	X
HIV-1 RNA low copy sample		X						X	

Procedure	Screening Visit ^a	Maintenance Phase							Withdrawal Assessments ^y
		Day 1 ^b	Month						
			2	4	6	8	10	12 ^{bb}	
CD4+ cell count	X	X	X	X	X	X	X	X	X
CD8+ cell count		X			X			X	X
Urinalysis ⁿ		X			X			X	X
Fasting Labs Glucose, Cholesterol (Total, HDL and LDL) and Triglycerides ^o		X			X			X	X ^p
Hepatitis B (HBsAg), Anti-HBc, and Anti-HBsAG, Hepatitis C (anti-HCV Ab)	X								
PT/PTT/INR	X	X							
Whole Blood (Virology)		X			X			X	X
CCI									
PBMCs ^q		X			X			X	X
Insulin, HbA1c and renal, and bone biomarker analytes (blood urine) ^r		X			X			X	X ^x
CCI									
Genetics sample ^t		X							
BIK Dispensation		X	X	X	X	X	X	X ^{aa}	
IP accountability (Pill Counts)			X	X	X	X	X	X	
HIV TSQ ^s ^{cc}		X			X			X	X ^{dd}
HIV TSQ ^c ^{cc}								X	X ^{dd}
CCI									
CCI									
History of Cosmetic procedures ⁹⁹								X	X

Time and Events Table for BIK to Oral Lead In – Extension Phase:

Procedure	Extension Phase				Withdrawal Assessments ^y	Long-Term Follow-up ^z
	Month					
	13	14	15	Q2M After Month 15		
Eligibility Verification (Inclusion/ Exclusion Criteria)	X ^d					
Symptom Directed Physical Exam and Medical Assessment ^f	X	X	X	X	X	X
Weight, Height and BMIs					X	
Waist Circumference					X	
Hip Circumference					X	
Vital Signs (BP, HR, Temperature) ^h					X	
12-lead ECG ⁱ					X	
HIV Associated Conditions	X	X	X	X	X	X
AEs, SAEs, Concomitant Medications	X	X	X	X	X	X
ISR Assessment for IM injection		X	X	X	X	X
Clinical chemistry and Hematology	X	X	X	X	X	X
Pregnancy Testing ^l	S	U	U	U	S	U
HIV-1 RNA and sample for storage (S) ^m	X	X	X	X	X	X
CD4+ cell count		X	X	X	X	X
CD8+ cell count					X	
Urinalysis ⁿ		X			X	
Fasting Labs Glucose, Cholesterol (Total, HDL and LDL) and Triglycerides ^o		X			X	
Whole Blood (Virology)					X	
CCI						
PBMCs ^q					X	

Procedure	Extension Phase				Withdrawal Assessments ^y	Long-Term Follow-up ^z
	Month					
	13	14	15	Q2M After Month 15		
PK sampling ^u (S)=Storage only		S	S		X	S
Oral CAB and Oral RPV Dispensation ^v	X					
IP accountability (Pill Counts)	X	X				
IM treatment administration ^w		X	X	X		
CCI						

Time and Events Table for BIK to Direct to Injection – Extension Phase:

Procedure	Extension Phase			Withdrawal Assessments ^y	Long-Term Follow-up ^z
	Month				
	13	14	Q2M After Month 14		
Eligibility Verification (Inclusion/ Exclusion Criteria)	X ^d				
Symptom Directed Physical Exam and Medical Assessment ^f	X	X	X	X	X
Weight, Height and BMI ^g				X	
Waist Circumference				X	
Hip Circumference				X	
Vital Signs (BP, HR, Temperature) ^h				X	
12-lead ECG ⁱ				X	
HIV Associated Conditions	X	X	X	X	X
AEs, SAEs, Concomitant Medications	X	X	X	X	X
ISR Assessment for IM injection	X	X	X	X	X
Clinical chemistry and Hematology	X	X	X	X	X
Pregnancy Testing ^j	S	U	U	S	U
HIV-1 RNA and sample for storage (S) ^m	X	X	X	X	X
CD4+ cell count		X	X	X	X
CD8+ cell count				X	
Urinalysis ⁿ		X		X	
Fasting Labs Glucose, Cholesterol (Total, HDL and LDL) and Triglycerides ^o		X		X	
Whole Blood (Virology)				X	
CCI					
PBMCs ^q				X	

Procedure	Extension Phase			Withdrawal Assessments ^y	Long-Term Follow-up ^z
	Month				
	13	14	Q2M After Month 14		
PK sampling ^u (S)=Storage only		S		X	S
IP accountability (Pill Counts)	X				
IM treatment administration ^w	X	X	X		
CCI					

Safety Follow Up Visit: Conduct approximately 4 weeks after the last dose of IP. Required only if the participant has ongoing AEs or lab abnormalities at the last on-study visit. This visit may be conducted by telephone.

Note: BP – Blood pressure, HR – Heart Rate, BMI – Body Mass Index, HDL – High Density Lipoprotein, LDL – Low Density Lipoprotein, PT - Prothrombin Time, PTT - Partial Thromboplastin Time, INR - International normalized ratio, PBMC – peripheral blood mononuclear cell, RNA – Ribonucleic acid, HbA1c = Glycated hemoglobin, HBsAg = hepatitis B surface antigen, HCV = hepatitis C virus, HIV-1 = human immunodeficiency virus type 1.

- a. Complete all Screening assessments within 35 days. Participants may begin the Maintenance Phase as soon as all Screening assessments are complete. Participants may be rescreened once and will be assigned a new participant number.
- b. For participants who elect to participate in the oral lead in period, oral CAB 30 mg + RPV 25 mg will be administered and the oral lead will start on Day 1. For participants who choose to go directly into injections, the first loading dose will be administered on Day 1. Visits for participants on the BIK arm are expected to occur every 56 days as projected according to the Day 1 visit. There is a ±3 day visit window, from the projected visit date (Maintenance Phase of the study).
- c. For participants who elect to participate in the oral lead in period, the first loading dose will be administered and the oral lead in will end. For participants who choose to go directly into injections, the second loading dose will be administered.
- d. Confirmation of eligibility to continue the Maintenance Phase, and eligibility to enter the Extension Phase.
- e. Collect full routine medical history plus (report at Baseline visit): HIV risk factors (may be collected at a later study visit), cardiovascular risk factors (assessments include smoking status and history, family history of cardiac events), recent [≤6 months] illicit drug use, intravenous drug use, gastrointestinal disease, metabolic, psychiatric, renal, bone, and neurologic disorders. At Month 11 (D21)/12 (OLI and BIK), assessments inclusive of smoking status, alcohol use and illicit drug use since the start of the study will be administered.
- f. Physical exams should be conducted as part of normal routine clinical care. Medical assessments include any decisions the study staff must make for participants management and/or care of participant.
- g. Height collected at Baseline Day 1 only. Recommended procedures to measure weight, waist and hip circumference can be found in protocol Section 10.10. Weight related measurements to be collected are weight, body fat %, total body water %, muscle mass, and bone mineral mass.
- h. Measure vital signs after about 5 minutes of rest in a semi-supine position.

- i. A 12-lead ECG will be performed after resting in a semi-supine position for at least 5 minutes. ECGs will be performed pre-dose. ECG pre-dose will be performed in triplicate at Day 1. A 2-hour post-dose ECG will also be performed at Day 1 (D2I), Month 1 (OLI) and Month 12 (OLI)/Month 11 (D2I) for participants receiving CAB LA + RPV LA with an allowable window of ± 30 minutes.
- j. Only SAEs related to study participation or to a concomitantly administered Viiv/GSK product will be collected between obtaining informed consent and administration of study drug at Day 1.
- k. On Day 1, the eC-SSRS is to be administered prior to randomization. The eC-SSRS will be completed at the beginning of the visit following administration of other PROs required prior to injections. The eC-SSRS is not required during the Withdrawal visit if withdrawal occurs during the Extension Phase.
- l. Women of childbearing potential only. S=serum, U=urine. Pregnancy events will be captured starting at Day 1 following initial exposure to study drug. Serum pregnancy test can substitute for urine pregnancy test if locally required but must be appropriately timed to confirm pregnancy status prior to randomization and first IM administration. If the urine test is positive, perform a serum test and do not administer injection. The frequency of pregnancy tests should be performed according to local legal requirements.
- m. Month 12 (OLI and BIK) and Month 11 (D2I) HIV-1 RNA retest (within 4 weeks) for results > 50 c/mL will be captured as unscheduled visit. Plasma for storage samples will be used for possible future analyses.
- n. A morning specimen is preferred. To assess biomarkers: urine albumin/creatinine ratio; urine protein/creatinine ratio; urine phosphate; beta-2-microglobulin; and retinol binding protein.
- o. An overnight fast is preferred; however, a minimum of a 6-hour fast is acceptable.
- p. Only collect if the Withdrawal visit occurs at Month 6 or Month 12 (OLI and BIK); Month 5 or Month 11 (D2I).
- q. Whole blood/PBMC collection samples may be used for virologic analyses. PBMCs will be collected at baseline Day 1, Month 6, Month 12, or Withdrawal if prior to Month 12 (OLI and BIK). PBMCs will be collected at baseline Day 1, Month 5, Month 11, or Withdrawal if prior to Month 11 (D2I)
- r. Blood sample for insulin, HbA1c, and renal and bone biomarker assessments: **Renal:** CystatinC; Beta-2-Microglobulin; Retinol Binding Protein (RBP); **Bone:** bone specific alkaline phosphatase, procollagen type 1-N-propeptide, type 1 collagen cross-linked C-telopeptide, osteocalcin, 25 hydroxy-Vitamin D.
- s. Blood sample for **CCI**
- t. Informed consent for genetic research must be obtained before sample collection. Sample may be collected at any visit after signing informed consent, but preferably at the Day 1 visit.
- u. **One blood sample for CAB and RPV each to be collected at each PK timepoint.** At Month 1, for participants who elected to participate in the Oral Lead in, and Month 14 for participants who were randomized to BIK and switched to CAB LA + RPV LA in the Extension Phase and will participate in the Oral Lead in, Pre dose PK samples are to be collected: PRIOR to the final oral dose of CAB + RPV. **For pregnant participants** (on CAB+RPV arm): two blood samples for CAB and one RPV sample at each PK timepoint. Refer to protocol Section 10.6.6.3.
- v. Participants who elected to participate in the Oral Lead in before switching to CAB LA + RPV LA injections, will take final dose of oral lead-in regimen in the clinic at the Month 1/Month 14 visit and begin injections.
- w. If possible, injections should be spaced approximately 2 cm from one another and from the site of any previous injection and or any injection site reaction. Bring RPV LA to approximately room temperature prior to injecting. Time and location of injection (right or left) as well as needle length used will be collected in the eCRF. The first injection can be performed before central lab results become available and safety parameters are reviewed.
- x. Collect sample for these assessments ONLY if the Withdrawal visit occurs at Months 6 and 12 (OLI and BIK); Month 5 and 11 (D2I).
- y. Refer to Section 7.1 of the protocol for additional information on performing withdrawal assessments
- z. Participants receiving one or more injections with CAB LA and/or RPV LA will be assessed with clinic visits at Months 3, 6, 9 and 12 during the Long-Term Follow-Up Phase
- aa. BIK dispensation (1-month supply) for participants who plan on entering into the Extension Phase. Participants who do not enter the Extension Phase or do not wish to transition to the commercial supply will not receive 1-month supply at M12.

CONFIDENTIAL

213500

- bb. Data from visit will be used to determine participant's eligibility to enter the Extension Phase of study. If participant elects to enter the Extension Phase, determine if the participant will elect to start injections immediately or start with oral lead in.
- cc. All PROs are recommended to be administered before other assessments and injections take place at each designated visit.
- dd. Only collected if Withdrawal visit occurs during the Maintenance Phase.

cc

A large black rectangular redaction box covers the text of item 'cc'.

- ff. When assessing CDC stage at Screening/Baseline, consider only the latest available CD4 T-cell count, except when the participant had an active Stage 3 event 6 months prior to Screening.
- gg. At Month 11 (D2I)/ Month 12 (OLI or BIK) or withdrawal, (depending which is sooner) participants will be asked if any cosmetic procedures were performed during the conduct of the study.

